Delivery of the SBIRT and HHC. Six or more clinical counselors/intake coordinators/research coordinators will be available in the PED to deliver the SBIRT and HHC⁴³ [ENREF 65](#) interventions. The use of clinical counselors/intake coordinators/research coordinators will increase the generalizability of the intervention, as most U.S. emergency departments have clinical counselors/intake coordinators/research coordinators available.

Resources for quitting marijuana use: Should participants report that they are current marijuana users, they will be offered information to help them quit marijuana use.

Setting. This study will occur in the main PED or in the Urgent Care of CCHMC.

Clinical Counselor/Intake Coordinator/Research Coordinator Activities, Training, and Monitoring

Three or more clinical counselors/intake coordinators/research coordinators will deliver the SBIRT intervention and three or more clinical counselors/intake coordinators/research coordinators will deliver the HHC intervention to caregivers while their child is waiting to be seen in the PED. All clinical counselors/intake coordinators/research coordinators will receive formal motivational interviewing (MI) training from an MI expert. This training, followed by booster session(s) after approximately 6 months or more, will teach them how MI can be used as a collaborative, person-centered form of guiding to elicit and strengthen motivation for change and will help them use specific skills related to MI. Clinical counselors/intake coordinators/research coordinators will be trained in MI strategies and techniques. The MI trainer will review a selection of audio recordings of each clinical counselor/intake coordinator/research coordinator chosen randomly throughout the study period and they will receive individualized feedback on these sessions from the MI trainer. The reviews will be spread out over the course of recruitment period. The clinical counselors/intake coordinators/research coordinators' audio-recorded sessions will be independently rated for adherence using the Motivational Interviewing Treatment Integrity (MITI) system by our MI expert, who will provide individualized written and verbal feedback to each clinical counselor/intake coordinator/research coordinator.⁴⁴ These audio-recorded sessions will be collected in an ongoing basis to facilitate fidelity to MI. MI approaches have been successfully applied in the ED setting for a variety of issues, including alcohol and smoking.⁴⁵

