
The clinical counselor/intake coordinator/research coordinator who delivers the SBIRT will be trained as a Tobacco Treatment Specialist at a TTS training center. This training will teach the clinical counselors/intake coordinators/research coordinators how to deliver an evidence-based, cognitive behavioral treatment for nicotine dependence. Presentations and hands-on exercises will emphasize the understanding the addictive nature of tobacco use, its impact on health, and key clinical activities for assessing and treating the nicotine dependent individual. The PI will then provide this clinical counselor/intake coordinator/research coordinator with an "Assisted Referral" training session focused on study logistics, the delivery of brief cessation and SHSe reduction

counseling, and direct connection to the QL, or smokefreeTXT, or smokefree.gov during the PED visit. The clinical counselors/intake coordinators/research coordinators will be taught to frame the messages to increase caregiver's risk perception of smoking to their child and themselves, and they will be trained to tailor the messages to motivation to quit and level of tobacco dependence.^{46,47} The clinical counselors/intake coordinators/research coordinators who deliver the HHC intervention will receive training from the PI or study staff on the purpose and importance of talking to caregivers about healthy habits to improve their child's health⁴³ [ENREF 65](#) and will be given guidance on engaging and delivering the intervention to caregivers during the PED visit; barrier identification and reduction techniques will be taught.

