During the approximately 48-month or longer study enrollment period, CRCs and approximately 1-2 pairs of clinical counselors/intake coordinators/research coordinators (i.e., one from each condition) will provide study coverage every weekday. This increases the opportunities for recruitment and delivery of the interventions. Our prior research demonstrates that approximately 3 CRCs will be more than adequate to recruit 750 caregivers. Enrollment times will represent peak PED volumes. CRCs will screen consecutive caregivers of patients presenting to the PED using CCHMC's EMR system, Epic. CRCs will identify caregivers by reviewing Epic records of registered patients. A secure database will be used which will include all patients, their age, gender, race, chief complaint, enrollment status, and reasons for non-enrollment.

Eligible caregiver adult participants must: 1) be > or equal to age 18; 2) be accompanying a child 0-17 years of age 2) be a daily smoker; 3) speak and read English (if shown to be efficacious, we will translate the intervention materials and test it with multi-lingual CRCs and clinical counselors/intake coordinators/research coordinators in a future trial), 4) have a permanent address and a working cell or landline number, 5) live within an approximately 50 mile radius of CCHMC (since we will conduct home visits.)

Eligible child participants must: 1) Not be a current smoker of tobacco or marijuana; 2) present to the PED with : (a) a stable condition, that is, patients who are not critically ill and do not require immediate treatment and intervention by the PED practitioner (triage levels 2-5) and (b) a potentially SHSe-related complaint (which will include complaints such as wheezing, difficulty breathing, cough, ear infection, cold, ear pain, runny nose, congestion, flu, asthma, shortness of breath) as outlined by the U.S. Surgeon General;⁴⁸ or SHSe-related discharge diagnosis.

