Preliminary Analyses. Univariate and bivariate examination of variables will be done first. Distributional properties of the continuous outcome variables will be examined. To control for non-normal distributions and heterogeneous error variances, we will use logarithmic transformation and report geometric means and associated 95% confidence intervals; this is particularly relevant for cotinine. We will conduct several preliminary analyses prior to addressing the Study Aims: (1) Examination for out of range values; (2) Comparison of baseline characteristics of caregivers and children across groups. If baseline differences are found, further analyses will include these variables as covariates in assessing caregiver and child outcomes as appropriate; and (3) Attrition analyses to assess if: Participants who were lost to follow-up are different from those retained. Although we do not expect differential attrition by group, it will be evaluated and if it occurs, we will weight the follow-up data to reflect the proportion assigned to each group. If key variables significantly predict attrition, we will examine the analysis with and without the drop-outs. Thus, we will compare our primary outcomes using a multiple imputation approach for missing data to allow maximum utilization of our data. When including those that were lost to follow-up, the outcome data may be weighted using a response propensity analysis^{94,95} which uses the baseline distributions on these variables so that follow-up data has the same distributions on these variables as the baseline data. For all analyses we shall include in the model an indicator variable to account for which clinical counselor/intake coordinator/research coordinator was involved in the delivery of the SBIRT or HHC.

General approach for addressing study aims. This is a two-group RCT, wherein caregivers are randomly assigned to the SBIRT Group vs. HHC group. The appropriate statistical models for analyses of data for inclusion of time dependent outcomes are General Linear Mixed Models (GLMM) for data either with a Gaussian/normal distribution or with a binomial or Poisson distribution, using the appropriate link function, invoking Generalized Estimating Equations (GEE) to account for the longitudinal aspect of the data.⁹⁶

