We will use GLMM to evaluate the relative effectiveness of the SBIRT versus HHC group on our primary outcomes: point prevalence and prolonged abstinence at 6-months. The analysis will be repeated with caregiver level differences between groups included as covariates. We will use mixed model analysis of covariance, with repeated measures to assess change (controlling for baseline differences between groups) to assess the effect of the SBIRT on secondary outcomes including reduction in use, number of quit attempts, and changes in readiness to quit. Kappa statistic will be used to assess agreement between the caregiver's self-report and the assessment of tobacco use based on expired carbon monoxide levels and/or salivary cotinine at 6 months. It is possible that use of and adherence to the NRT will influence outcomes in the intervention group. In addition, some of the participants in the control condition may obtain NRT during the study interval. We will examine NRT use or dose, defined as self-reported adherence, as a covariate in order to control for this possible relationship.

Analyses for Primary Aims 1-3.

Primary Aim 1, Hypothesis 1: We hypothesize that SBIRT participants will have higher prolonged abstinence and point prevalence cessation rates compared to those in the HHC group. As stated above, our primary approach to the analysis is using multiple imputation, with clinical counselors/intake coordinators/research coordinators included in the model. We shall then use analysis of covariance, to control for any baseline differences of caregivers between conditions. In addition we will also control for motivation to quit, considered a priori as a potential covariate, using the score on the contemplation ladder. As we are stratifying on motivation to quit and caregiver gender, we will initially enter this into the model as an interaction. To address child cotinine as the 6-month outcome, we will use a t-test and then an analysis of covariance to incorporate the variables different at baseline. Incorporating the 6-week outcome values, we will use GLMM invoking GEE for the repeated

measures and also a model including covariates. This approach will be used to assess the intervention's effect on abstinence and point prevalence and child cotinine.

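### Counsellor indicators beside the arm term, with separate counsellors per arm, leave the SBIRT-versus-HHC effect undefined; nest counsellor in arm and name the contrast

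*Combined protocol and SAP*

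**What the plan says.** The combined protocol and SAP, Analytic Plan, Preliminary Analyses, sets a general rule: "For all analyses we shall include in the model an indicator variable to account for which clinical counselor/intake coordinator/research coordinator was involved" in delivering SBIRT or HHC. Primary Aim 1, Hypothesis 1 repeats it for abstinence: "our primary approach to the analysis is using multiple imputation, with clinical counselors/intake coordinators/research coordinators included in the model". The target of that analysis is the arm comparison: "We will use GLMM to evaluate the relative effectiveness of the SBIRT versus HHC group on our primary outcomes". The general approach adds GEE for one purpose only, "invoking Generalized Estimating Equations (GEE) to account for the longitudinal aspect of the data".

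On staffing, the section on counsellor activities, training and monitoring says that three or more counsellors "will deliver the SBIRT intervention and three or more clinical counselors/intake coordinators/research coordinators will deliver the HHC intervention". It gives the two groups different preparation. SBIRT staff are trained as tobacco treatment specialists, whereas for the control condition "The clinical counselors/intake coordinators/research coordinators who deliver the HHC intervention will receive training from the PI or study staff". Participant Screening, Enrollment, and Exclusion describes pairs of counsellors ("i.e., one from each condition) will provide study coverage every weekday").

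No section says whether the counsellor term is fixed or random, whether counsellor is nested in arm, or how the arm effect is formed once counsellors are in the model.

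**The concern.** An indicator variable ordinarily means a fixed 0/1 column for each level. If each counsellor works in one arm only, knowing the counsellor tells you the arm, so the counsellor indicators already carry everything in the arm column. A model with both cannot separate them. The coefficient meant to answer the main efficacy question then either does not exist or depends on which column the software removes.

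An analyst will probably notice this. The repair, however, involves choosing the coding, the weights and the scope of inference, and as the plan stands those choices would be made with the abstinence data in hand. Because the rule covers all analyses, the same gap affects smoking bans, child cotinine and the secondary outcomes.

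**Working it through.** **Inputs.** Three or more counsellors per arm (counsellor activities section). 300 analysed per group after 20% loss, or 375 under multiple imputation (Sample Size; Table 2). HHC and SBIRT rates of 6.3% and 12% for point prevalence, and 2.1% and 7% for prolonged abstinence (Estimate of effect sizes). The plan states no alpha or sidedness with its power figures; two-sided 0.05 is assumed unless noted. Layouts with 4 and 6 counsellors per arm, and equal caseloads, are also assumptions.

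**The plan's own power figure.** The plan states 80% power for a 6.4-point increase with 300 per group. That is 6.3% vs 12.7%, an odds ratio of (0.127/0.873)/(0.063/0.937) = 2.16, as in Table 2. The two-proportion formula gives 76.3% two-sided and 81.4% one-sided with continuity correction; only the latter is within two points of 80%. The plan's power text makes no allowance for a counsellor term.

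**Rank.** With k counsellors per arm, the columns are one intercept, one arm and 2k − 1 counsellor indicators, 2k + 1 in all. Participants fall into only 2k distinct counsellor cells, so the rank cannot exceed 2k.

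| Counsellors per arm | Columns | Rank | Rank without the arm column |
|---|---|---|---|
| 3 | 7 | 6 | 6 |
| 4 | 9 | 8 | 8 |
| 6 | 13 | 12 | 12 |

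Removing arm leaves the rank unchanged, so arm adds nothing and its coefficient is not estimable.

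**If a column is dropped by default.** The surviving arm coefficient compares the reference counsellor in one arm with the reference counsellor in the other. With 3 per arm that is 100 vs 100 participants instead of 300 vs 300, and the standard error is √3 = 1.73 times larger. Use power = Φ[(d√n − 1.96√(2p̄(1 − p̄))) / √(p1(1 − p1) + p2(1 − p2))].

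- 6.3% vs 12%, n = 300: (0.987 − 0.799)/0.406 = 0.46, power 68%. With n = 100: (0.570 − 0.799)/0.406 = −0.56, power 29%.
- 2.1% vs 7%, n = 300: (0.849 − 0.578)/0.293 = 0.93, power 82%. With n = 100: (0.490 − 0.578)/0.293 = −0.30, power 38%.

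**A contrast that works.** Let counsellor j in an arm have n_j participants and x_j abstainers. The caseload-weighted arm average is Σ(n_j/n)(x_j/n_j) = x/n, the arm's overall proportion. Without other covariates, the contrast is therefore the ordinary risk difference. In simulation (200,000 trials per setting, 3 per arm) it gave 69.0% and 84.6% power, against 68.9% and 84.6% for the score test with no counsellor term. These are slightly above the formula's 68% and 82%, which is an approximation. With the 8 randomisation strata kept (assumed 80% female, four equal stages), power was 68% and 84%.

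**Why the weights and scale need naming.** Equal weighting of counsellors loses information when caseloads differ. For an assumed 180/90/30 split, the effective size is 9/(1/180 + 1/90 + 1/30) = 180 per arm instead of 300. Averaging counsellor log-odds also breaks down at low rates. At 2.1%, an HHC counsellor with 100 participants has no abstainers with probability 0.979^100 = 0.120, and at least one of three does with probability 1 − (1 − 0.120)^3 = 32%. The same arithmetic gives 60% with four counsellors of 75 and 92% with six of 50.

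**The case against.** The strongest reply is that the plan's framework already allows for this. The general approach names mixed models, and the power section refers to hierarchical linear modeling; with counsellor as a random effect, the arm effect is estimable. That is a fair reading of what is permitted. But the power section defines no levels, GEE is tied only to repeated measurement, and the one sentence describing the counsellor term calls it an indicator variable. The reply shows that a sound analysis is compatible with the text, not that the text specifies one.

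Second, strict separation of the teams is inferred. No sentence stops a counsellor from covering both conditions, and any crossover makes the matrix full rank. The arm coefficient would then rest on the crossed sessions. With an assumed 30 or 60 of 600 sessions crossed, its standard error is about 2.3 to 2.8 or 1.7 to 2.5 times larger, depending on how the sessions are spread.

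Third, the primary approach is multiple imputation, which Table 2 pairs with 375 per group. Power without a counsellor term would then be at most about 78% and 91%. This stands, but it does not affect the rank result.

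A reader might infer that the primary analysis must fail, or that counsellor clustering invalidates the test. The documents support neither. The first needs both fixed indicators and no cross-cover, and the fault would probably be spotted. The second needs an intraclass correlation, which the documents do not give, and a claim reaching beyond these counsellors.

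**Conclusion.** The point holds as a gap in specification with a definite consequence. Under the natural reading of the counsellor term and of the staffing sections, the SBIRT-versus-HHC coefficient is not estimable: the design is one short of full rank in every nested layout checked. Under the other readings it is estimable, but the plan does not say which applies. The result rests on fixed indicators and on each counsellor serving one arm.

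It does not show that the trial lacks a valid analysis, since a caseload-weighted contrast recovers the whole-arm comparison at about 69% and 85% power with 300 per arm. Fixed or random is a choice of scope, and both are defensible. The plan does expect wide use ("The use of clinical counselors/intake coordinators/research coordinators will increase the generalizability of the intervention"), so it should say which population of counsellors the conclusion covers. It should be fixed before analysis.

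**What to change.** In Preliminary Analyses, and by reference in Primary Aim 1, replace the plain indicator with wording to this effect, for all outcomes including Aim 2 and the secondary outcomes:

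- Counsellor is nested within study arm. If anyone delivers both conditions, counsellor-by-arm cells are used.
- The treatment effect is the caseload-weighted difference between the SBIRT and HHC arm averages, computed in each imputed data set and pooled. It is never a contrast between individual counsellors.
- For binary outcomes, report the risk difference, and convert the arm-average probabilities to an odds ratio to match Table 2.
- The inference is for the participating counsellors. A model with a random counsellor effect and a model with no counsellor term are sensitivity analyses.

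The cost is wording and a little programming; no new data are needed. The drawback is a conclusion limited to these counsellors.

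The random-effect analysis will be weak with so few counsellors, so a non-significant result there should not be over-read. As a guide, a counsellor-level t-test with 3 per arm at 6.3% vs 12% has 46% power with no counsellor variation and 20% at an assumed intraclass correlation of 0.02. If the fixed analysis were nevertheless generalised to other counsellors, its Type I error with 3 per arm would be 11% to 26% for assumed correlations of 0.005 to 0.02. The limit on inference should therefore be stated explicitly.
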